### **8.4.4 Adherence and Retention Analyses**

Adherence to the study will be analyzed by collecting the pill bottles at the first postoperative visit.

### **8.4.5 Baseline Descriptive Statistics**

Baseline characteristics including age, sex, ASA class, BMI, past medical and surgical history will be recorded by melatonin and placebo group for THA and TKA cohort separately. Summary statistics will be used, where means and standard deviations will be reported for continuous variables, and count and proportion will be calculated for categorical variables. Inferential tests to assess differences in baseline characteristics of the groups will be performed using ANOVA or the Wilcoxon rank sum test if the normality assumption does not hold for continuous variables, and the Chi-square test for categorical variables. All tests will be two-sided with a significance level at 0.05.

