# **Statistical Considerations**

## **8.1 Statistical Hypotheses**

- Primary endpoint: The null hypothesis is that there is no difference between the melatonin and placebo group in the mean ESS score from days 1-14 postoperatively. The alternative hypothesis is that there is a difference between the melatonin and placebo group in the mean ESS score during any of these time points
- Secondary endpoints:
  - Hours of sleeping measured each day from days 1-14 for overnight sleep: The null hypothesis is that there is no difference between the melatonin and placebo group in the mean hours of sleeping at these time points. The alternative hypothesis is that there is a difference between the melatonin and placebo group in the mean hours of sleeping at these time points. Nighttime awakenings are those that require an additional dose of pain medication to go back to sleep.
  - Other secondary endpoints to be listed

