### **8.4.2 Analysis of the Secondary Efficacy Endpoints**

The secondary endpoints include number of total hours of sleep, number of nighttime awakenings, and narcotic consumption.

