### **8.4.6 Additional Sub-Group Analyses**

Subgroup analyses of the primary and secondary endpoints will be done on the subgroups of THA vs TKA with ANOVA, and all other categorical variables will be analyzed using Fisher's Exact Test. All tests will be two-sided with a significance level of 0.05.

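### Baseline characteristics are significance-tested between randomized arms, while the primary ESS model adjusts for no baseline variable

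*Combined protocol and SAP*

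**What the plan says.** Section 8.4.5 lists the variables: "Baseline characteristics including age, sex, ASA class, BMI, past medical and surgical history will be recorded by melatonin and placebo group", separately for the THA and TKA cohorts. The list is open. After summary statistics, the section adds: "Inferential tests to assess differences in baseline characteristics of the groups will be performed using ANOVA or the Wilcoxon rank sum test" for continuous variables, "and the Chi-square test for categorical variables", and "All tests will be two-sided with a significance level at 0.05". It does not say what follows from a significant result.

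Section 8.4.1 compares ESS over days 1-14 between arms, within each cohort, by repeated measures ANOVA. No baseline covariate is named. Section 8.5.1 uses block randomization and rules out stratification by age, gender or surgery type, although section 8.3 has the two cohorts analysed separately. Section 8.4.7 marks multiplicity as not applicable.

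A baseline sleep measure does exist. Section 6.2.2 records PROMIS Sleep Disturbance at Visit 1, and the schedule in section 6.2 places the Epworth scale in the surgery column. Neither is on the 8.4.5 list.

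Section 8.4.6, on subgroups, adds that "all other categorical variables will be analyzed using Fisher's Exact Test". The secondary endpoints in section 8.4.2 are described thus: "The secondary endpoints include number of total hours of sleep, number of nighttime awakenings, and narcotic consumption". None of these is categorical as named, but section 8.1 leaves the list open: "Other secondary endpoints to be listed".

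**The concern.** If randomization is properly carried out, any baseline difference between arms is due to chance, so each test examines a null hypothesis already known to be true. A p-value below 0.05 invites doubt about sound randomization, or unplanned adjustment. A p-value above 0.05 invites the reading that the arms are balanced. Neither reading says whether an imbalance matters, because that depends on how strongly the variable predicts ESS, which the test does not measure.

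What would deal with a prognostic imbalance is adjustment fixed in advance, and the plan has none. Because allocation is not stratified by surgery type, blocking does not enforce balance within either analysed cohort. At stake are a misleading baseline table and precision that could be had at almost no cost.

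**Working it through.** **Inputs from the plan.** Target difference 2.65 and SD 5.3, 64 per arm in each cohort, two-sided 0.05, 80% power (section 8.2); six named baseline characteristics in each of two cohorts (section 8.4.5).

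**Input not in the plan.** The correlation rho between a baseline covariate and ESS. It is assumed here over 0.1 to 0.7.

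**1. The plan's sample size.** The standardized effect is 2.65/5.3 = 0.50. The normal approximation gives 63 per arm. With the noncentral t distribution, 63 per arm gives 79.5% power and 64 gives 80.1%. The plan's 64 is reproduced and is not in question.

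**2. Chance findings.** For k independent tests at 0.05, P(at least one) = 1 - 0.95^k.

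- One cohort, k = 6: 1 - 0.95^6 = 26.5%, with 6 × 0.05 = 0.3 false positives expected.
- Both cohorts, k = 12: 1 - 0.95^12 = 46.0%, with 0.6 expected.
- If the history items expand the list to 20 tests in all (an assumption): 64.2%, with 1.0 expected.

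**3. What passes as balanced.** At 64 per arm, the smallest significant standardized difference is t(0.975, 126 df) × sqrt(2/64) = 1.979 × 0.1768 = 0.350. An observed imbalance of 0.30 SD gives p = 0.092.

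**4. Effect on the ESS comparison.** An imbalance of d SD shifts the expected arm difference, in one direction or the other, by rho × d × 5.3. The standard error of the arm difference is 5.3 × sqrt(2/64) = 0.94. For d just under 0.35:

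| Assumed rho | Shift (points) | Share of 2.65 | Type I error given that imbalance |
|---|---|---|---|
| 0.1 | 0.19 | 7% | 5.3% |
| 0.3 | 0.56 | 21% | 8.0% |
| 0.5 | 0.93 | 35% | 13% |
| 0.7 | 1.30 | 49% | 21% |

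The last column is P(|Z| > 1.96) with Z normal, mean rho × 0.35/sqrt(2/64) and variance 1 - rho². It is conditional on the imbalance. Averaged over all randomizations, the unadjusted test keeps its 5%.

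**5. What adjustment would gain.** Adjusting for the covariate reduces the SD to 5.3 × sqrt(1 - rho²). By normal approximation, power = Φ(2.65/(SD × 0.1768) - 1.96):

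- Unadjusted: Φ(2.828 - 1.96) = 80.7%.
- rho = 0.3: SD 5.06, power 84%.
- rho = 0.5: SD 4.59, power 90%.

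Steps 4 and 5 treat ESS as one value per patient with SD 5.3, as section 8.2 does.

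**The case against.** The strongest reply is that nothing in the plan depends on these tests. Section 8.4.5 attaches no action to a p-value, section 8.4.1 does not refer to them, and the unadjusted comparison is valid over repeated randomizations. This stands. A reader might infer that the primary test's error rate is compromised; the documents do not support that.

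It can also be said that the summaries already planned show the size of any imbalance. That is true, and it is why the p-values add nothing.

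A third reply is that the shift in ESS rests on a correlation that the plan does not give. This also stands. A reader might infer that the tests miss imbalances large enough to change the ESS result. At rho 0.1 the shift is negligible. At rho 0.5 it is 0.93 points, about one standard error, and an imbalance of 0.30 SD or more on a given variable arises in only about 9% of randomizations. No section shows that age, sex, ASA class, BMI or history predicts ESS.

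The 46% pools two cohorts that are analysed separately and assumes independence, although age, ASA class, BMI and medical history plausibly overlap. The per-cohort 26% is the fairer figure for one baseline table. In the other direction, the list is open and the count may rise.

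On Fisher's exact test, a reader might conclude that the rule is an error because no named endpoint is categorical. The text does not go that far: section 8.1 leaves endpoints to be added, and section 8.4.3 reports adverse event severity and relationship, which are categorical. The scope of the rule is undefined, which calls for clarification and not deletion.

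**Conclusion.** The point holds as one of reporting and efficiency. The baseline tests can flag only chance differences: about a 26% chance of at least one per cohort and 46% over both, with six independent tests in each. They say nothing useful about imbalances under 0.35 SD, whose effect on the ESS difference ranges from minor (7% of the target at rho 0.1) to substantial (49% at rho 0.7).

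The more important gap is the lack of prespecified adjustment. Filling it would raise power from about 80% to about 84% at rho 0.3 or 90% at rho 0.5. These gains depend on correlations that the documents do not give. The primary test's overall type I error and the sample size are not affected. The Fisher clause is a minor matter of wording.

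**What to change.** - **Section 8.4.1:** prespecify adjustment of the primary model for a baseline sleep score. The one clearly recorded at baseline is PROMIS Sleep Disturbance (section 6.2.2). A pre-operative ESS would serve if the Epworth scale in the surgery column of section 6.2 is completed before surgery, which the plan should state. Age, sex and ASA class are optional further covariates. Fix the list in advance and keep it whatever balance is observed. Since section 11.3.2 allows enrolment after surgery on the same day, state that the score must be recorded before randomization.
- **Section 8.4.5:** replace the inferential tests with the descriptive summaries already planned, adding standardized differences and the baseline sleep score.
- **Section 8.4.6:** name the variables to which Fisher's exact test applies, and how that rule relates to the chi-square rule in 8.4.5.

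The cost is SAP wording and a few degrees of freedom. Sample size and visits do not change. With PROMIS as the covariate nothing new is collected; a pre-operative ESS would add one questionnaire if it is not already taken then.

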#### **8.4.5.1 Efficacy Review**

Planned interim analyses of the primary endpoint will not be performed.

### **8.4.6 Additional Sub-Group Analyses**

Subgroup analyses of the primary and secondary endpoints will be done on the subgroups of THA vs TKA with ANOVA, and all other categorical variables will be analyzed using Fisher's Exact Test. All tests will be two-sided with a significance level of 0.05.

### **8.4.7 Multiple Comparison/Multiplicity**

Not applicable

### **8.4.8 Tabulation of Individual Response Data**

Individual participant data will be listed by measure and time

## **8.5 Measures to Minimize Bias**

### **8.5.1 Enrollment/Randomization/Masking Procedures**

Research assistants not involved in the study protocol will be responsible for maintaining the patient database and randomization algorithm. Treatment will begin on postoperative day zero. The control groups will receive 14 placebo pills. The treatment group will receive 14 pills of 5mg melatonin. Patients will begin taking a daily pill for 14 days postoperatively. They will continue to receive their selected treatment during their inpatient hospital stay.

Block randomization will be done through RedCap to ensure equal distribution of intervention vs control subjects. The block size will be undisclosed. There will be no stratification based on age, gender, or surgery type.

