## Protocol Summary

Title	MELATONIN USE AFTER PRIMARY TOTAL JOINT ARTHROPLASTY: A RANDOMIZED, DOUBLE BLIND, PLACEBO-CONTROLLED TRIAL
Brief Summary	The purpose of this study is to determine the effect of melatonin supplementation on patient sleep quality, length of stay, and opioid consumption following primary, unilateral, elective total hip or knee arthroplasty.
Phase	N/A
Objectives	The primary objective is improved sleep quality postoperatively
Methodology	Single Center, randomized, double-blind, placebo-controlled clinical trial
Endpoint	The primary endpoint will be enrollment and completion of the study of 256 patients as pre-determined by statistical analysis.
Study Duration	Approximately 12 months (post IRB approvals)
Participant Duration	We estimate each patient will need to participate for roughly 60 days
Duration of IP administration	Patients will take the melatonin or placebo for 14 days
Population	Sample size will be 252 patients, both male and female patients will be included, all adult patients undergoing primary elective TKA or THA will be included. No vulnerable populations will be enrolled
Study Sites	Langone Orthopedic Hospital, New York, NY NYU Brooklyn Hospital, Brooklyn, NY
Number of participants	256 participants
Description of Study Agent/Procedure	Melatonin is an over-the-counter sleep aid
Reference Therapy	None
Key Procedures	Pre- and postoperative sleep survey, survey on quality of sleep, patient reported outcome questionnaires, narcotic consumption and pain daily for 14 days postoperatively
Statistical Analysis	Descriptive statistics will be used to report baseline characteristics and primary study objectives

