## **3 Study Design and Endpoints**

### **3.1 Description of Study Design**

This will be a single-center randomized double blind placebo control clinical trial. In the cohort of patients undergoing primary elective total hip and the cohort of patients undergoing primary elective knee arthroplasty, participants are recruited from those who are willing to consent and participate in the study, and will be randomly 1:1 divided into intervention group and placebo group.

Knee cohort:

- Intervention group will receive a 5mg Melatonin prescription for 14 days
- Control group will receive a placebo pill for 14 days

Hip cohort:

- Intervention group will receive a 5mg Melatonin prescription for 14 days
- Control group will receive a placebo pill for 14 days

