#### **4.5 Total Number of Participants and Sites**

252 patients will be recruited at NYU Langone Orthopedic Hospital and NYU Brooklyn Hospital.

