##### **4.6.2 Handling of Participant Withdrawals or Termination**

Any patient that wishes to withdraw or in whom a clinical adverse effect is noticed, will be allowed to do so without recourse. They will still be given appropriate standard of care follow-up as would be given any pre- or post-operative TJA patient. If a patient is presumed lost to follow-up they will be contacted via phone-calls and certified letters, which will be tracked. There is no safety risk predicted from abrupt termination. Any patients who withdraw or discontinue early will be replaced via recruitment of new patients. As LOH is a high-volume arthroplasty center performing thousands of primary TJA procedures there is not expected to be an issue in recruiting new subjects as approximately 10-50% of patients are projected to be affected by malnutrition (previously cited data).

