## **8.2 Sample Size and Power**

The overall study sample size is based on the primary endpoint of ESS measured at days 1-14. The MCID of the ESS is 2.65 and the SD is 5.3 based on previous literature. We assume the MCID and ESS values are the same for both THA and TKA cohorts. 64 patients are needed in the control and intervention groups separately for a two-sided alpha = 0.05, 80% powered study based on an ANOVA for the comparison of the ESS at days 1-14 between the control and intervention group, which provides us a total of 128 patients for THA cohort and TKA cohort separately.

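### Section 8.2 needs 128 hip and 128 knee patients, but 4.5 recruits 252 in all and no recruitment, replacement or randomisation rule secures either joint's number

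*Combined protocol and SAP*

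**What the plan says.** **Size required.** Section 8.2 states that "64 patients are needed in the control and intervention groups separately", "which provides us a total of 128 patients for THA cohort and TKA cohort separately". Section 8.3 keeps the two joints apart in every analysis, and 8.4.1 compares the arms within each joint. The power claim is therefore made once per joint.

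**Numbers to recruit.** Section 4.5 reads "252 patients will be recruited at NYU Langone Orthopedic Hospital and NYU Brooklyn Hospital". The Summary's Population row agrees ("Sample size will be 252 patients"). The Summary's Endpoint row instead refers to "completion of the study of 256 patients as pre-determined by statistical analysis", and its Number of participants row also gives 256. None of these places splits the total by joint.

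**Replacement.** Section 4.6.2: "Any patients who withdraw or discontinue early will be replaced via recruitment of new patients". It does not say which joint the new patient should have.

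**Randomisation.** Section 3.1 introduces the 1:1 division with "In the cohort of patients undergoing primary elective total hip and the cohort of patients undergoing primary elective knee arthroplasty" and lists an intervention and a control group under each joint. Section 8.5.1 uses permuted blocks of undisclosed size and adds: "There will be no stratification based on age, gender, or surgery type".

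**The concern.** Two things do not fit together. First, 252 cannot fill four groups of 64, so the number in the section that governs recruitment is not the number that the sample size section derives. Second, the target is per joint, but nothing in the recruitment, replacement or randomisation text is. No passage says when a joint is full, and a withdrawn hip patient could be replaced by a knee patient.

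What is at stake is the reading of each joint's result. If one joint finishes short and shows no difference, the 80% in 8.2 does not describe the test that was done there, and a larger sample in the other joint does not help because the two are not pooled.

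The missing surgery-type stratum is a lesser part. Unstratified blocks balance the arms overall and leave the arms within a joint to chance.

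**Working it through.** **Inputs.** From 8.2: difference 2.65, SD 5.3, two-sided alpha 0.05, power 80%, two groups, same values for both joints. Standardised effect d = 2.65 / 5.3 = 0.5. The documents give no hip/knee mix, no dropout rate and no within-patient correlation.

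**Method.** Power of the two-sample t-test (a two-group ANOVA at a single comparison): noncentral t with 2n − 2 degrees of freedom and noncentrality d × √(n/2), where n is patients per arm.

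**Step 1: the plan's own figure.** Solving for 80% gives n = 63.8, rounded up to 64, with power 80.15%. So 2 × 64 = 128 per joint and 2 × 128 = 256 in all. Section 8.2 reproduces, and it matches the Summary's 256.

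**Step 2: the 252.** 252 / 4 = 63 per arm, which is 256 − 252 = 4 patients short overall. At n = 63 the power is 79.5% per joint. This step assumes an even split by joint and arm.

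**Step 3: if recruitment ran to an overall 256 without regard to joint.** The mixes are assumptions. Arms are taken as equal within each joint.

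| Mix | Smaller joint, per arm | Power | Larger joint, per arm | Power |
|---|---|---|---|---|
| 50/50 exactly | 64 | 80.15% | 64 | 80.15% |
| 55/45 | 256 × 0.45 / 2 = 57.6 | 75.8% | 70.4 | 83.8% |
| 60/40 | 256 × 0.40 / 2 = 51.2 | 70.7% | 76.8 | 86.8% |

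If each patient is equally likely to be a hip or a knee, the hip count is Binomial(256, 0.5). Exactly 128/128 then occurs in about 5% of trials. The smaller joint averages 121.6 patients and 78.0% power, and the larger joint averages 82.0%. A joint named in advance averages 80.0%.

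**Step 4: stratification alone.** Fix each joint at exactly 128 and let the arm split within a joint vary by chance, approximated as hypergeometric (256 patients, 128 per arm, 128 in the joint). The 95% range for one arm is 56 to 72. Power at 56/72 is 79.5%, and the average over all splits is 79.99%. Against 80.15% the loss is 80.15 − 79.99 = 0.16, or about 0.2 points.

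**Step 5: how far this carries to the planned analysis.** Section 8.4.1 plans a repeated measures ANOVA over days 1-14, whereas 8.2 computes a single comparison. As an illustration, suppose ESS were taken on all 14 days and patient means compared, with a common correlation ρ. The SD of a patient mean is then 5.3 × √((1 + 13ρ)/14). For the smaller joint at 60/40 (51.2 per arm):

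| ρ (assumed) | SD of mean | Power |
|---|---|---|
| 0.5 | 3.88 | 92.8% |
| 0.7 | 4.50 | 83.9% |
| 0.9 | 5.05 | 74.9% |
| 1.0 | 5.30 | 70.7% |

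The gain cannot be relied on, because the schedule in 6.2 lists the Epworth only at surgery and Visit 2.

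**The case against.** The best defence is that the target is already stated. Section 8.2 gives 128 for each joint, 256 is exactly twice that, and a fair reader can take the overall number as the sum of two cohort targets whose closing rule was left unwritten. This largely stands. A reader might infer that the plan means to stop at a pooled count regardless of joint, but no passage says so. That reading comes from silence, and the Step 3 figures are conditional on it. The defence does not explain the 252, and it does not supply the missing rules.

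A reader might also infer that 3.1 and 8.5.1 contradict each other outright. Section 3.1 implies a 1:1 division within each joint but does not state separate randomisation lists, and unstratified 1:1 blocks still give 1:1 within a joint in expectation. Not stratifying is an explicit design choice. It brings no bias and no inflation of type I error.

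The larger losses rest on assumed mixes. With a true 50/50 intake, chance alone gives 60/40 or worse in about 0.1% of trials, so 70.7% needs a genuinely unequal intake, which the documents do not show. The 78.0% also describes whichever joint turns out smaller; a joint chosen in advance averages 80.0%.

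Finally, it would be too strong to say that a joint has 80% power only if it reaches 64 per arm. That is true of 8.2's single-comparison calculation. The repeated measures analysis could do better, by an amount the documents do not let anyone compute.

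**Conclusion.** The point holds and should be fixed. The part that needs no assumption about the joint mix is that 4.5 and one Summary row recruit 4 fewer patients than 8.2 requires, and that no passage carries the per-joint target into recruitment, replacement or randomisation. At an even split the shortfall itself is worth about 0.6 points of power (80.15 − 79.52 = 0.63).

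The larger exposure is conditional: if recruitment ran to an overall total, the smaller joint would have 78.0% on average under a chance 50/50 intake, 75.8% at 55/45 and 70.7% at 60/40. These are single-comparison figures on 8.2's inputs, not the power of the repeated measures ANOVA. Cohort size is the main risk, and stratification is a cheap secondary improvement. The validity of the comparison within either joint is not in question.

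**What to change.** 1. **Section 4.5 and every Summary row that gives a number:** *256 patients (128 THA, 128 TKA; 64 per arm in each), plus replacements.*
2. **Section 4.6.2:** *A patient who withdraws or discontinues early is replaced by a new patient with the same joint. The withdrawn patient stays in the intent-to-treat population.*
3. **Section 8.5.1, in place of the no-stratification sentence:** *Randomisation is 1:1 in permuted blocks of undisclosed size, stratified by surgery type (THA, TKA) and not by age or gender. A replacement takes the next allocation on the list for that joint. Each joint closes when 128 patients plus its replacements have been randomised.*
4. **If joint sizes will not be enforced,** restate 8.2 so that 80% power (single-comparison calculation) applies only to a joint that reaches 64 per arm, and give the power at the smallest joint size expected.

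Items 1 and 3 belong together, because stratifying balances the arms within a joint but does not by itself bring the joint to 128.

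**Cost.** One stratification variable in REDCap, a running count per joint, and the wording edits. The joint is known before randomisation. One joint may close to recruitment before the other. A replacement need not fall in the withdrawn patient's arm, and a last block may be incomplete, so completers may not be exactly 64 per arm. As an assumed example, since the block size is undisclosed, 62/66 would still give 80.1%.
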